2.2 Secondary Objectives

2.2.1 To compare the effect of aspirin versus placebo in early stage HER2 negative breast cancer patients upon:

- a) Distant disease-free survival
- b) Overall survival
- c) Cardiovascular disease (see [Section11.3](#))

2.2.2 To compare the toxicity of aspirin versus placebo in early stage HER2 negative breast cancer patients.

2.2.3 To assess adherence to aspirin and placebo among early stage HER2 negative breast cancer patients.

2.2.4 To bank tumor and germline deoxyribonucleic acid (DNA), plasma and urine collected at baseline and sequential plasma and urine collected 2 years later for future measurement of inflammatory markers.

2.2.5 To determine if there are subgroups of participants characterized by lifestyle factors associates with greater inflammation for whom there is greater benefit of aspirin versus placebo upon iDFS.

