8.2.2.2 Grade 2 bleeding

For grade 2 bleeding, one level dose reduction will be required.

For recurrent Grade 2 bleeding after dose reduction, discontinue protocol therapy.

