8.2.2.3 Grade 3 and 4 gastrointestinal bleeding or active gastrointestinal ulceration

Grade 3 and 4 GI bleeding will require that the patient be permanently removed from protocol treatment.

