9.1 Routine Adverse Event Reporting

Adverse event data collection and reporting, which are required as part of every clinical trial are done to ensure the safety of patients enrolled in the studies as well as those who will enroll in future studies using similar agents. Adverse events are reported in a routine manner at scheduled times according to the study calendar in Section 5.0. For this trial, the Adverse Events: Solicited form is used for routine AE reporting in Rave.

Solicited Adverse Events: The following adverse events are considered "expected" and their presence/absence should be solicited, and severity graded, at baseline and for each cycle of treatment.

• CTCAE v 4.03 Term	• CTCAE v4.0 Organ Class (SOC)
• Gastrointestinal bleeding	• Gastrointestinal disorders
• Intracranial hemorrhage	• Nervous system disorders
• Epistaxis	• Respiratory, thoracic and mediastinal disorders
• Hematuria	• Renal and urinary disorders
• Dyspepsia	• Gastrointestinal disorders
• Gastritis	• Gastrointestinal disorders
• Bruising	• Injury, poisoning and procedural complications

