13.3.3 Analysis plans for primary and secondary endpoints

The primary analyses of iDFS will be performed in an intention-to-treat manner, in which all patients including those who do not begin protocol therapy will be analyzed according to their assigned arm. The primary determination of efficacy will be a time-to-event analysis using the Kaplan-Meier method for estimation, and the stratified log-rank test of iDFS to compare the aspirin arm versus the placebo arm (with stratum defined by hormone receptor status, BMI and stage), using the nominal alpha defined by the group sequential design, as given in [Section 13.4.2](#). A secondary analysis to estimate efficacy will use a multivariate Cox proportional hazard model to evaluate differences between arms after adjusting for stratification factors and the additional covariates of known importance to breast cancer including age, tumor size, and number of involved nodes. Identical models will be used to evaluate differences between arms in DDFS and OS.

Planned subgroup analyses will evaluate the hazard ratio of aspirin to placebo in subgroups defined by the study stratifiers of hormone-receptor status and enrollment time (HR positive and enrolled \leq 18 months from time from diagnosis vs HR positive and enrolled $>$ 18 months from diagnosis vs HR negative) and body-mass index (less than 30 kg/m^2 vs at least 30 kg/m^2). In addition to the WHO thresholds for underweight ($<18.5 \text{ kg/m}^2$), normal weight ($18.5\text{-}24.9 \text{ kg/m}^2$), overweight ($25\text{-}29.9 \text{ kg/m}^2$) and obese ($\text{BMI} \geq 30 \text{ kg/m}^2$), we will explore a linear association in the multivariate Cox model, based on the findings of Ligibel et al. that the prognostic relationship to disease-free survival with adjuvant chemotherapy was linear across the entire range of BMI observed at baseline. Further, an exploratory analysis will evaluate whether baseline factors are predictive of difference in clinical benefit of aspirin over placebo using multiplicative interactions in the Cox model. All tests of secondary objectives will use a two-sided Type I alpha of 0.05, and point estimates will be reported with 95% confidence intervals taken from Cox models.

Analyses of toxicity will be conducted on patients who receive at least one dose of aspirin or placebo. Toxicity will be reported by type and maximum grade using CTCAE v4.03 and contrasts of aspirin to placebo will use Fisher exact tests.

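### The only planned toxicity contrast, Fisher tests on maximum grade, ignores time on drug and is distorted if that time differs by arm

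*Combined protocol and SAP*

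**What the plan says.** Comparing toxicity is a stated secondary objective (section 2.2.2): "To compare the toxicity of aspirin versus placebo in early stage HER2 negative breast cancer patients". Section 13.3.3 defines the population, "Analyses of toxicity will be conducted on patients who receive at least one dose of aspirin or placebo", and the method, "Toxicity will be reported by type and maximum grade using CTCAE v4.03 and contrasts of aspirin to placebo will use Fisher exact tests". It names no grade cut-off for the Fisher test and no exposure time, time to event or cumulative incidence for toxicity. The same section uses time-to-event methods for iDFS, DDFS and OS.

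On data capture, section 9.1 says of the solicited events that "their presence/absence should be solicited, and severity graded, at baseline and for each cycle of treatment". The adverse-event row of the study calendar (section 5.0) is marked before registration, every 6 months and at end of treatment, and is blank for post-treatment follow-up. Section 9.2, however, collects possibly, probably or definitely related grade 3-5 events on a late form more than 30 days after the last dose. It also lets its other adverse-event form apply in clinical follow-up. Section 9.3.1 keeps related serious events reportable after 30 days.

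Drug is stopped for several reasons. Section 8.2.2.2 says "For recurrent Grade 2 bleeding after dose reduction, discontinue protocol therapy", and section 8.2.2.3 says "Grade 3 and 4 GI bleeding will require that the patient be permanently removed from protocol treatment". Sections 8.2.4 and 8.2.6 stop treatment for intracranial bleeding and for related tinnitus or hearing loss. Section 7.3 stops it at recurrence or a new invasive primary. Section 1.6.1 expects similar adherence in both arms.

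**The concern.** A maximum-grade table treats a patient observed on drug for a few months like one observed for four years. Time on drug will vary. Accrual runs 30 months and the final analysis is at month 54 (section 13.2), so potential time is 24 to 54 months before any early stop. If one arm stops sooner, it has less time in which routine grading can record an event, and the Fisher contrast reads that shortfall as lower toxicity.

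A difference by arm is plausible in either direction. Aspirin may cause more stops under section 8.2, and a stop for one toxicity ends scheduled grading of the others, such as dyspepsia, gastritis, bruising and epistaxis. If aspirin works, placebo patients stop sooner for recurrence. This comparison is the risk half of the benefit-risk answer, so its estimate should not depend on who stayed on tablets longer.

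**Working it through.** **The plan's own figures.** The documents give no event rate, power or stopping rate for toxicity. The nearest stated figure is the iDFS event count: 4 × (1.960 + 0.842)² / (ln 0.75)² = 4 × 7.85 / 0.0828 ≈ 380, against 381 stated. Exponential iDFS with the stated accrual and loss gives 381.2 events at month 54 (215.9 placebo, 165.3 aspirin; the plan says 216 and 165) and a mean potential follow-up of 37.5 months. The size and follow-up used below therefore match the plan.

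**Common event, simple model.** From the plan: 1468 per arm (2936 / 2) and potential time of 24 to 54 months, taken as uniform (2 to 4.5 years). Assumed, because the documents give no values:
- event rate *h* = 0.035 per year on placebo and 0.035 × 1.25 = 0.04375 on aspirin;
- stopping rate *s* = 0.06 per year on placebo, and 0.06, 0.10 or 0.15 on aspirin.

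With constant hazards and *k* = *h* + *s*, the chance of an event recorded on drug is

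p = (h/k) × {1 − [e^(−2k) − e^(−4.5k)] / (2.5k)}.

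Placebo: k = 0.095, so p = 0.368 × (1 − 0.736) = 0.0972.

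| Aspirin stopping per year | p on aspirin | Observed ratio (formula) | Observed ratio (simulated) | Fisher power (simulated) |
|---|---|---|---|---|
| 6% | 0.1199 | 1.23 | 1.24 | 47% |
| 10% | 0.1126 | 1.16 | 1.16 | 26% |
| 15% | 0.1043 | 1.07 | 1.08 | 9% |

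The simulated column averages ratios over trials and so sits slightly above the formula. A person-time rate test on the same data has 49-51% power throughout. For an event that aspirin does not affect (*h* = 0.035 in both arms), p on aspirin is 0.0972, 0.0913 or 0.0846, so the ratio reads 1.00, 0.94 or 0.87 (simulated 1.00, 0.95, 0.88).

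**How large a stopping gap this needs.** Still on drug at 5 years: e^(−0.30) = 74% on placebo, against e^(−0.50) = 61% or e^(−0.75) = 47% on aspirin. The gaps are 13 and 27 points.

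**The documents' own compliance figures.** Section 1.6.1 cites 73.7% placebo and 72.5% aspirin in a primary-prevention trial, and 81% and 84% in an adenoma meta-analysis. As a rough proxy, treat these as the share on drug at 5 years, so s = −ln(share)/5. That gives 0.0610 and 0.0643, then 0.0421 and 0.0349. The same formula returns ratios of 1.23 and 1.25, which is almost no bias.

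**Adding recurrence stops.** Including the plan's iDFS hazards (77% at 5 years, HR 0.75) raises the three simulated ratios to 1.26, 1.18 and 1.10. Earlier recurrence on placebo pushes the other way, as expected.

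**Rare and common events on the plan's follow-up distribution, with recurrence stops.** Toxicity rates are assumed. The columns give the excess of aspirin patients off drug at 5 years; each cell gives Fisher power, then power of an exposure-adjusted rate test.

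| Assumed placebo rate, true ratio | Equal | 10 points | 20 points |
|---|---|---|---|
| 0.4%/year, 2.0 | 59%, 60% | 52%, 59% | 45%, 58% |
| 0.4%/year, 1.5 | 20%, 23% | 17%, 23% | 13%, 22% |
| 5%/year, 1.3 | 79%, 74% | 63%, 74% | 42%, 73% |

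The true 2.0 is seen as 2.03, 1.94 and 1.85. For rare bleeds most of the missing power is there even with equal stopping.

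**Which effect measure.** If events cluster early (assumed hazard 2.5 times in year 1 and 0.3 times afterwards) and aspirin stopping is 10% or 15%, the person-time ratio drifts to about 1.30-1.36 for a true 1.25. An unaffected event reads 1.03-1.07. The Cox hazard ratio stays near 1.25.

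**The case against.** A reader might infer that grading stops with study drug, that the stopping rules hide aspirin's harm, and that the trial will therefore understate it and often miss it. The documents do not support that chain.

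- Collection does not stop outright. Related grade 3-5 events and related serious events are still captured (sections 9.2 and 9.3.1). The clear gap is later grade 1-2 events and later grade 3-5 events judged unrelated or unlikely related.
- A bleed that triggers a stop is already recorded. Only time at risk for other toxicities, or for a later higher grade, is lost.
- The rules bind both blinded arms, and recurrence stops can work in the opposite direction.
- No excess stopping on aspirin is documented, and the cited compliance implies almost none.

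Nor does the plan yield only a p-value. Proportions by type and grade will be available by arm, and on-treatment incidence under the protocol's stopping policy is a legitimate question.

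All of this stands, and it makes the size of the bias conditional. It does not remove the gap, because equal time on drug is never checked in the toxicity analysis. The compliance summary in section 13.4.1 covers patients on treatment at each visit, so it does not show who has stopped. The primary-prevention trial used 100 mg every other day, which is weak support for equal stopping at 300 mg daily; the adenoma data are closer.

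**Conclusion.** The concern holds in conditional form. The single toxicity contrast in section 13.3.3 takes no account of time on drug and is distorted whenever that time differs by arm. With assumed stopping of 10% or 15% per year on aspirin against 6% on placebo, a true ratio of 1.25 for a common event reads about 1.16 or 1.08. With equal stopping, or with the compliance the documents cite, there is almost no bias. For rare severe bleeds the method matters less than the small number of events, and no change of test cures that. These sizes rest on constant hazards, on stopping that is independent of the event, and on toxicity and stopping rates that the documents do not give. The documents do not show that aspirin's harm will be understated.

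**What to change.** In section 13.3.3, for each solicited event type at grade 2 or worse and at grade 3 or worse:
- Add a comparison of time to first on-treatment event, from first dose to 30 days after last dose, with a Cox hazard ratio, 95% CI and cumulative incidence by arm. Say how death and early stopping enter the cumulative incidence.
- Use the hazard ratio, not a constant-rate person-time ratio, as the effect measure, because the latter is biased if events cluster early.

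Also report treatment discontinuation by arm and reason, so that readers can judge whether stopping differed and whether it was related to toxicity. Keep the maximum-grade table with Fisher tests alongside, and state its grade cut-offs. Reconcile sections 5.0, 9.1 and 9.2 on what is collected after treatment ends.

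Extending the contrast to all follow-up is not a substitute. If risk falls back to the placebo level after stopping, a true on-drug ratio of 2.0 reads 1.85 instead of 2.03 at equal stopping (assumed placebo rate 0.4% per year).

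The cost is SAP wording and some programming. Onset of solicited events may be known only to the 6-month visit interval, so event times are approximate. Power may be slightly lower if exposure is equal: in the 5% per year example the rate test had 74% against 79% for Fisher.

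### Toxicity is contrasted only by type, so no planned test gives a patient-level bleeding comparison across sites for objective 2.2.2

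*Combined protocol and SAP*

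**What the plan says.** Section 2.2.2 sets a formal between-arm objective: "To compare the toxicity of aspirin versus placebo in early stage HER2 negative breast cancer patients". Section 13.3.3 defines the population, "Analyses of toxicity will be conducted on patients who receive at least one dose of aspirin or placebo", and then the method: "Toxicity will be reported by type and maximum grade using CTCAE v4.03 and contrasts of aspirin to placebo will use Fisher exact tests". The same section fixes the level for secondary tests: "All tests of secondary objectives will use a two-sided Type I alpha of 0.05".

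Section 9.1 lists seven solicited adverse events, for which "their presence/absence should be solicited, and severity graded, at baseline and for each cycle of treatment". Five of the seven concern bleeding, each in its own organ class:

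- gastrointestinal bleeding (gastrointestinal)
- intracranial hemorrhage (nervous system)
- epistaxis (respiratory)
- hematuria (renal and urinary)
- bruising (injury and procedural complications)

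The dose rules, by contrast, treat bleeding as one graded entity whatever the site. Section 8.2.2.2 reads: "For grade 2 bleeding, one level dose reduction will be required". No section defines an any-bleeding or major-bleeding outcome for analysis, and none gives a bleeding rate, a target effect or a power figure for toxicity.

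**The concern.** Section 1.1 justifies the trial by the need to weigh the risks of aspirin against its benefits, and the solicited list shows that bleeding is the main harm anticipated. As written, the bleeding evidence will be a set of separate rows, each with its own p-value. No rule says which row answers objective 2.2.2, and the toxicity sentences specify no effect estimate: the confidence intervals in 13.3.3 come from Cox models. The cardiovascular endpoint does not fill the gap, because 11.3.2 counts hemorrhagic and ischemic stroke together.

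A composite could be built after unblinding, but choosing its sites and grades with the data in hand invites selective reporting. Fixing it beforehand avoids that and gives one interpretable estimate for the benefit-risk statement.

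**Working it through.** **The plan's own figures.** There is none to reproduce for toxicity. The only powered comparison is invasive disease-free survival (13.2). The Schoenfeld formula at hazard ratio 0.75, one-sided 0.025 and 80% power gives 380 events, against the stated 381; power at 381 events is 80.2%.

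**Inputs.** From the documents: 2936 patients randomized 1:1 (13.1, 13.2), so at most 2936/2 = 1468 treated per arm; two-sided alpha 0.05 and Fisher exact tests (13.3.3). Assumed, because the documents are silent: four bleeding sites with equal placebo risk p of 0.25%, 0.5% or 1%, independent of each other, and a common rate ratio (RR) of 1.5 or 2.

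**Formulas.**
- Single-row power π: exact enumeration of the two-sided Fisher test.
- At least one of four rows significant: 1 − (1 − π)^4.
- Composite risk: 1 − (1 − p)^4 on placebo and 1 − (1 − RR·p)^4 on aspirin, then Fisher power by the same enumeration.

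Example at p = 0.5%, RR 2: π = 27.1%, so at least one row is 1 − 0.729^4 = 72%. The composite risks are 1 − 0.995^4 = 1.99% and 1 − 0.99^4 = 3.94%, giving 86%.

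| RR | Placebo risk per site | One row | At least one of four rows | Composite |
|---|---|---|---|---|
| 2 | 0.25% | 12% | 40% | 55% |
| 2 | 0.5% | 27% | 72% | 86% |
| 2 | 1% | 56% | 96% | 99% |
| 1.5 | 0.25% | 4% | 16% | 18% |
| 1.5 | 0.5% | 9% | 32% | 36% |
| 1.5 | 1% | 18% | 55% | 65% |

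The gain from the second-last to the last column is about 2 to 15 percentage points. With no treatment effect, the chance of at least one significant row is about 6% to 12% over these risks; for the composite it is 3% to 4%.

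**Unequal risks.** Assume placebo risks of 0.3% intracranial, 1% gastrointestinal, 2% epistaxis, 1% hematuria and 5% bruising, with RR 1.5. Single-row powers are 5.4%, 18.3%, 36.6%, 18.3% and 78.0%.
- Without bruising, at least one row: 1 − 0.946 × 0.817 × 0.634 × 0.817 = 60%; composite 68%.
- With bruising: 1 − 0.400 × 0.220 = 91%; composite 96%.

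**Overlap.** If patients who bleed at more than one site cut the composite risk by a quarter, composite power at RR 2 falls to 42%, 74% and 96%. That is close to the 40%, 72% and 96% for at least one independent row, although correlation would lower the row figure too.

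**Serious bleeding.** A grade 3 or higher composite with 1% placebo risk would have about 18% power at RR 1.5 and 56% at RR 2.

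**What is collected.** The routine reporting table in section 9.2 requires unsolicited grade 3 to 5 events at any attribution, but unsolicited grade 2 events only when at least possibly related. More than 30 days after last treatment, the Late form takes only grade 3 to 5 events at least possibly related.

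**The case against.** The best defense is that reporting toxicity by type and maximum grade is a coherent plan. Type is not defined in 13.3.3, and nothing there forbids a grouped bleeding row. Gastrointestinal bleeding is already a single solicited term, so those sites are not split, and the DSMB reviews adverse events twice a year (13.4.1). All of this stands. It makes the point an improvement rather than a contradiction, but it does not supply a prespecified bleeding comparison.

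Three stronger readings are tempting and not supported.

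- A reader might set one row against the composite (12% against 55%, or 27% against 86%) and conclude that the plan would probably miss a real doubling. But the plan tests every row, so the fair comparator is at least one significant row. At 1% per site and RR 2, all four rows would miss only about 4% of the time (0.445^4).
- A reader might infer that the toxicity objective has little power for bleeding in general. The documents give no rates, so this cannot be shown. One row alone has 78% power at 5% placebo risk with RR 1.5, and 88% at 2% with RR 2. Low power is a matter of rare types, at about 1% or less.
- A reader might infer that everything needed for any composite is already collected. That fails for unsolicited grade 2 bleeding, which is filtered by attribution. Pooling it with solicited terms, which are asked about whatever their cause, would mix two collection rules.

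**Conclusion.** The gap holds: 13.3.3 provides no patient-level bleeding contrast across sites, although the solicited data would support one. Prespecifying it is a worthwhile, low-cost improvement to the analysis of objective 2.2.2. It does not touch the primary endpoint.

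The benefit is moderate: about 2 to 15 points of power over at least one of four rows in the equal-risk scenarios, a lower false-positive rate, and one interpretable estimate. The size rests on assumed risks, a common rate ratio and independent sites; positive correlation would reduce it. It matters mainly for rare bleeding types. A composite that includes bruising may draw much of its power from minor events, and a composite restricted to serious bleeding may stay underpowered, so its confidence interval will say more than its p-value.

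**What to change.** In 13.3.3, prespecify for objective 2.2.2, among patients who received at least one dose, the proportion with any-site bleeding by maximum grade per patient:

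- (a) grade 2 or higher, using the solicited bleeding terms only;
- (b) grade 3 or higher, using the solicited terms plus any other hemorrhage reported from registration to 30 days after last treatment.

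For each, report the risk difference with its 95% CI alongside the Fisher test, and keep the site-specific rows as supporting description. These limits keep each composite within what section 9 collects without an attribution filter.

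The cost is a short addition to the analysis text and one derived variable (maximum bleeding grade per patient), with no new forms or patients. The downside is that a composite mixes sites of unequal importance; the two grade thresholds and the retained rows address that.

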13.4 Study Monitoring and Interim Analysis

13.4.1 Study monitoring

Interim monitoring will be conducted by the Alliance Data and Safety Monitoring Board (DSMB) and will be scheduled to coincide with the semi-annual calendar of the board's meetings. Under standard monitoring procedures, the DSMB will consider evidence regarding safety (adverse events, adherence) and the feasibility of completing the trial (accrual rate).

Adherence will be reported to the DSMB using descriptive statistics to summarize by arm compliance to study treatment and non-protocol use of aspirin and NSAIDs. For compliance, the proportion that completed 80% of the total number of study tablets over the past period (6 months) and a 95% confidence interval will be reported for the number of patients on treatment at each study visit. P-values from a two-sided Fisher exact test will

be provided to the DSMB to help with interpretation of the data, but they are not considered as formal hypothesis tests and will not trigger any decision rule on study status.

In addition, formal interim analyses are to be conducted to consider early stopping for futility. These interim analyses are timed to occur after 50% of the total number of iDFS events are observed in order to be sensitive to the known heterogeneity of recurrence rates over time for the two subpopulations of triple negative versus HmR-positive breast cancer, in which the former disease tends to recur earlier than the latter disease. Therefore, there will be no early stopping for superiority of aspirin over placebo in order to be able to fully address the question of treatment effect by breast cancer subtype.

